11.3 Baseline treatment values

ADA status measured in serum and ADA antibody serum sample results for immunogenicity measurements at day 0 pre-dose will serve as baseline.

11.4 Adjustment for covariates

N/A.

11.5 Handling of dropouts or missing data

see sec. 9 - Handling of drop-outs or missing data.

11.6 Interim analysis and data monitoring

There are no planned interim analyses for this study.

11.7 Examination of subgroups

Special attention in analyses is laid on ADA-positive and ADA-negative patients at baseline. Incidence of treatment-induced ADA patients and treatment-boosted ADA patients is determined by baseline ADA result.

Stratification by age class, gender and race will be done for the primary and secondary immunogenicity endpoints.

11.8 Multiple comparison/multiplicity

No adjustment for multiplicity is made in this study.

11.9 Multicenter studies

No subgroup analyses by center will be done for evaluating the primary or secondary endpoints.

12. METHODS OF PRIMARY IMMUNOGENICITY, KEY SECONDARY AND SECONDARY ENDPOINT ANALYSES

Tabulations will show results for FAS and PPS population.

12.1 Analyses of the primary immunogenicity endpoint overall ADA incidence

The overall ADA incidence will be derived from the number of patients having an ADA-positive sample during the course of the trial. Determination of the number of patients will include counting:

1. Patients, who were ADA-negative at baseline and ADA-positive after drug administration (**=treatment-induced ADA patients**)
2. Baseline ADA-positive patients with significant increases (≥ 5 -fold) in ADA titer after drug administration (**= treatment-boosted ADA patients**)

Both patient numbers will be summed up for the overall ADA incidence nominator. The nominator will be derived by dividing by the number of evaluable patients (see sec. Definitions: Evaluable patients = *A subject with at least one sample taken after drug administration during the treatment or follow-up that is appropriate for ADA testing (with reportable result).*). Patients, who were baseline positive patients without any samples available after drug administration, will be excluded from the number of evaluable patients. Note that for ADA-positive patients unscheduled dosing visits are performed and results from those visits have to be respected as well.

Numbers and percentages (defined as above) of incidences in each treatment group, incidence difference between dasiglucagon and GlucaGen® with its 95% exact confidence limits will be provided. The tabulation will be replicated using stratification factors sex, age class and race.

12.2 Analyses of the key secondary immunogenicity endpoints

12.2.1 Treatment-induced ADA incidence

For presenting the treatment-induced incidence only **treatment-induced ADA patients** will be used. Incidence is based on subjects that were ADA-negative at baseline. Tabulations will follow the same strategies/ models as for the key primary endpoint.

12.2.2 Treatment-boosted ADA incidence

For presenting the treatment-boosted incidence only patients falling under the second point in the section of the key primary immunogenicity endpoint will be used. Incidence is based on patients being ADA-positive at baseline. Tabulation will present the same statistics as for the key primary endpoint.

12.3 Analyses of further secondary immunogenicity endpoints

12.3.1 Incidence and titer of neutralizing activity of ADA-positive patients

Confirmed positive antibody samples will be further evaluated for in vitro dasiglucagon and/or glucagon neutralizing potential. The in vitro neutralizing effect will be evaluated in validated cell-based assays. In case of a positive result in the neutralizing antibody assays, a titer will be estimated.

Based on all samples taken, number of ADA-negative and number of ADA-positive samples will be displayed with counts/ percentages by treatment group. The calculation will differentiate between Day 0 (pre-dose/ baseline) and the other visits (post-dose/treatment, follow-up and unscheduled ADA positive visits). In addition the number and percentage of patients with positive/ negative ADA samples will be calculated and displayed by treatment group and the timely distinction as mentioned above. Patients included in the tabulation are the ones, who have a reportable pre-dose/ baseline ADA sample.

Pre-existing ADA-positive patients: Titer and boosting

Descriptive statistics will be presented for the neutralizing antibody titers Nab (reciprocal of the highest dilution factor, without unit) at Day 0 and the other visits (post-dose/ treatment and follow-up) by treatment group based on all measurements for patients being baseline ADA-positive. Descriptive statistics for tabulations will include additionally the interquartile range. Tabulation will include only patients being baseline ADA-positive.

Treatment-induced ADA-positive patients: ADA titer

Tabulations will be the same as for the pre-existing ADA, however only patients being ADA-negative at baseline will be respected.

Display of descriptive statistics will be done in case sufficient data are available. In any case data are displayed in listings.

12.3.2 Incidence of cross-reactivity of ADA positive patients towards endogenous glucagon

Cross-reactivity of ADA positive patients towards endogenous glucagon will be measured by a special laboratory. The following parameters will be available to evaluate cross-reactivity:

Samples from confirmed positive anti-dasiglucagon antibody patients (treatment-induced or treatment-boosted) will be further evaluated for potential cross-reactivity towards endogenous glucagon. The samples will be tested in the screening and confirmatory assays, in case of a confirmed positive result, a titer will be estimated. The number of anti-dasiglucagon positive patients that have antibodies that cross react with endogenous glucagon will be determined over the entire study.

Counts and percentages for this cross-reactivity parameter for all ADA-positive patients will be presented by treatment group.

12.3.3 Kinetics of ADA: The timing and duration of detected ADA response

1) Kinetics of patients being baseline ADA-negative

For analyses of kinetics of patients being baseline ADA-negative, patients being baseline ADA-positive will be excluded.

The following parameters will be derived:

- **Onset of ADA and number of drug applications:** Time until onset of ADA will be determined using the date of initial administration of the drug and the date of first date of detection (=date of blood sampling) of treatment-induced ADA in days (after Day 0/ baseline). Number of drug applications until first onset of ADA will be determined as well. A drug application is seen as being successfully applied in case the question on trial administration has been answered with 'yes'. All dosing visits as well as the unscheduled visits for ADA-positive patients have to be taken into account.
- **Duration of ADA:** Time between first onset of an ADA-positive result until its return to negativity/ no detectability. For calculation only antibody samples after the day 0 pre-dose sampling will be used. In case of having more than one ADA positive result, time point after the last ADA-positive result will be taken to evaluate return to negativity.

Listings

All parameters mentioned above under onset of ADA and duration of ADA will be provided in a listing for each patient. A footnote will indicate that only ADA-negative patients at baseline have been respected in this display.

Figures

Individual display of patients: For each of the ADA post-dose positive patients a line plot will be generated plotting time (date of ADA sample) versus titer. If possible the referring nominal visit will be included in the time axis as well. A reference line indicating the cut-off for positivity of the titer will be included in the figure (cut-off is 10 (minimum required dilution in the assay)). Patient ID and treatment group will be displayed. Line plots will display titers on original scale and on log scale. If possible for each patient original and log scale display will be shown in a panel display.

2) Kinetics of patients being baseline ADA-positive

For analyses of these kinetics, only patients being baseline ADA-positive will be included.

The following parameters will be derived:

- **Onset of ADA and number of drug applications:** Time until onset of ADA will be determined using the date of initial administration of the drug and the date of first onset (date of blood sampling) of treatment-boosted ADA in days (= significant increases (≥ 5 -fold) in ADA titer after Day 0/ baseline). Number of drug applications until first onset of ADA will be determined as well. A drug application is seen as being successfully applied in case the question on trial administration has been answered with 'yes'. All dosing visits as well as the unscheduled visits for ADA-positive patients have to be taken into account.
- **Duration of ADA:** Time between first onset of an ADA-positive boost result (= significant increases (≥ 5 -fold) in ADA titer after Day 0/ baseline) until its return to baseline titer < 5 -fold. For calculation only antibody samples after the day 0 pre-dose sampling will be used. In case of having more than one ADA positive result, the time point after the last ADA-positive (boost) result will be taken to evaluate return to negativity.

Listings

All parameters mentioned above under onset of ADA and duration of ADA will be provided in a listing for each patient. A footnote will indicate that only ADA-positive patients at baseline have been respected in this display.

Figures

Individual display of patients: For each of the ADA baseline positive patients a line plot will be generated plotting time (date of ADA sample) versus titer. If possible the referring nominal visit will be included in the time axis as well. A reference line indicating the cut-off for positivity of the titer will be included in the figure (cut-off is 10 (minimum required dilution in the assay)). Patient ID and treatment group will be displayed. Line plots will display titers on original scale and on log scale using e.g. a panel display.

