7.5.6 Unscheduled visit for ADA positive patients

A patient with a treatment induced or treatment boosted ADA response at visit 3-7 must be called in for an unscheduled visit. The procedures of this visit will be identical to the procedures performed at Visit 4 including administration of trial medication and assessments of pharmacodynamic and pharmacokinetic responses.

The visit should be scheduled as soon as the investigator is informed about a positive ADA result. The investigator should instruct the patient of the same dosing day requirements as for the regular dosing visits (Section 7.5.2) and instruct the patient to aim of having a similar sized breakfast and corresponding rapid acting insulin dose as prior Visit 2 and Visit 4.

A patient with a treatment induced or treatment boosted ADA response will be monitored until the ADA levels return to baseline.

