7.6.1 Immunogenicity measurements

Antibodies against dasiglucagon/glucagon will be measured at all visits after screening. During the treatment period (Visits 2, 3, and 4) samples will be collected pre-dose as well as at unscheduled dosing visits for ADA positive patients.

The ADA samples will be analyzed at a special laboratory (refer to Appendix 1). Samples collected at the planned visits will be analyzed in batches at three occasions during the trial and any positive results will immediately be communicated to the investigator in a blinded manner.

The clinical ADA assays have been validated in accordance with existing guidelines and recommendations.^{6,7,8,9,10}

Confirmed positive anti- dasiglucagon antibody samples, (treatment-induced or treatment-boosted) from anti-dasiglucagon antibody-positive patients will be evaluated for binding titer neutralizing potential and titer as well as cross-reactivity towards endogenous glucagon.

No further serum sampling will be needed as the ADA samples can be used for Nab analysis.

The *in vitro* neutralizing effect of antibodies will be measured using an assay^{9,12} based on glucagon receptor transfected human embryonic kidney cells. The calculated sensitivity in previous studies was about 51.8 ng/mL. The assay was also validated for recombinant glucagon with similar results.^{11,12} In case of a positive result in the Nab assay, a titer estimation will be performed. The cell-based Nab analyses will be performed by a special laboratory, BioAgilytix, Durham, NC, USA.

In vivo neutralizing effect will be evaluated by comparing PK and PD endpoints between ADA positive and ADA negative patients, further investigation may be performed by correlating ADA titer with PK and PD endpoints.

Residual and additional antibody serum samples may be stored until approval of market authorization by the health authorities. Further characterization of the antibody response may be requested by the health authorities.

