	16.2.6.1	Immunogenicity measurements	
	16.2.6.2	Antibody serum sample for immunogenicity measurements	
	16.2.6.3	Neutralizing antibody measurements (NAb titer)	
	16.2.6.4	Overall ADA incidence, treatment-induced ADA incidence, treatment boosted ADA-incidence	derived data

ICH Heading	Listing Number	Listing Description	Comment
	16.2.6.5	Kinetics: Timing and duration of detected ADA response	derived data
16.2.7		Adverse events and safety endpoints	
	16.2.7.1	Adverse events	
	16.2.7.1.1	Adverse events – CRF entries	
	16.2.7.1.2	Adverse events – MedDRA coding	
	16.2.7.1.3	Study-drug related adverse events (ADRs)	
	16.2.7.1.4	Serious adverse events	
	16.2.7.1.5	Deaths	
	16.2.7.1.6	Vital signs related to clinical events of interest	
	16.2.7.1.7	Injection site reactions	
	16.2.7.2	Local tolerability	
	16.2.7.3	Vital signs including change from baseline	incl. derived data CFB
	16.2.7.4	Body measurements	
	16.2.7.5	Physical examination and changes	
	16.2.7.6	12-lead ECG including change from baseline	
	16.2.7.7	Previous and concomitant medication	
16.2.8		Laboratory	
	16.2.8.1	Hematology including change from baseline	incl. derived data CFB
	16.2.8.2	Biochemistry including change from baseline	incl. derived data CFB
	16.2.8.3	Coagulation	
	16.2.8.4	Urinalysis including change from baseline	incl. derived data CFB
	16.2.8.5	Child bearing potential and pregnancy test	
	16.2.8.6	History of alcohol or drug abuse, alcohol breath test and urine drug screen	
16.2.9		Pharmacokinetics and pharmacodynamics	
	16.2.9.1	Plasma dasiglucagon and GlucaGen measurements	
	16.2.9.2	Individual PK metrics	derived data
	16.2.9.3	Plasma glucose measurements	
	16.2.9.4	Individual PD metrics	derived data
16.2.10		Comments	

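### SAP 12.3.3 does not split ADA duration at the extra dose given to responders, so a listed duration can join a resolved response to a re-challenge response

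*SAP*

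**What the plan says.** SAP 12.3.3 handles kinetics separately for patients negative and positive at baseline. For the baseline-negative group, duration starts at the first positive sample and ends at return to undetectable. If there is more than one positive, the "time point after the last ADA-positive result will be taken to evaluate return to negativity". All antibody samples later than the Day 0 pre-dose sample are used. The baseline-positive group follows the same pattern, with a 5-fold rise over baseline titer in place of positivity: "the time point after the last ADA-positive (boost) result will be taken to evaluate return to negativity". Neither rule mentions the extra dose.

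Under onset and number of drug applications, the same section says: "All dosing visits as well as the unscheduled visits for ADA-positive patients have to be taken into account".

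Protocol 7.5.6 calls back every treatment-induced or treatment-boosted responder from Visits 3 to 7 as soon as the site learns of the result. On content it says: "The procedures of this visit will be identical to the procedures performed at Visit 4 including administration of trial medication". On follow-up it says: "A patient with a treatment induced or treatment boosted ADA response will be monitored until the ADA levels return to baseline". Protocol 7.6.1 sets the testing schedule, "Samples collected at the planned visits will be analyzed in batches at three occasions during the trial", and the sampling time on dosing days, "samples will be collected pre-dose as well as at unscheduled dosing visits for ADA positive patients".

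The derived durations go to listing 16.2.6.5, "Kinetics: Timing and duration of detected ADA response". For kinetics, SAP Appendix C otherwise plans only individual titer figures.

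**The concern.** The extra dose is triggered by the reporting of a result, not by the patient's ADA status on the day. Testing is in batches, so a short response can have cleared before the dose is given. If a later sample is then positive, the end of the single duration moves beyond it, and the antibody-negative interval in between is counted as response time. The shift runs one way only, towards a longer duration.

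Timing and duration of ADA is a named secondary endpoint. Protocol 7.2 justifies the Day 35, 60 and 104 visits as following the expected peak and decline after the three scheduled doses, and a re-challenge inside that window disturbs that picture. Protocol 5.2 also attaches different clinical consequences to persistent and to transient antibodies.

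The placement of the SAP's instruction suggests an oversight. Unscheduled dosing visits are to be considered for onset and for applications up to onset. The extra dose cannot change either of these, because it is given only after a response has been found. Duration is the kinetic parameter it can change, and there the SAP has no provision for it.

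**Working it through.** **Inputs.** Visit windows from Protocol Table 2-1: Day 7 ±1, Day 14 ±1, Day 35 ±2, Day 60 ±5, Day 104 ±10. Duration rule from SAP 12.3.3. Extra dose from Protocol 7.5.6. Planning figures of 45 completers per arm and 5% incidence from SAP 5. The documents give no batch dates and no patient data, so every sequence below, including the extra-dose days, is assumed.

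**The plan's own figure.** ln(0.10)/ln(0.95) = 44.9, rounded up to 45; 1 − 0.95^45 = 0.9006. The 45 reproduces. It matters here only for the expected number of responders.

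**Can the dose come after clearance?** The synopsis of the current protocol puts the first patient's first visit in May 2017, and SAP 4 puts the last visit in February 2018, about nine months. Three evenly spaced batches (an assumption) would be about 9/3 = 3 months apart. A lag of weeks between a positive sample and the extra dose is therefore plausible.

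**Rule applied.** Duration = day of the first sample after the last positive − day of the first positive. The split version applies the same rule separately to samples up to and including the extra-dose pre-dose sample, and to later samples. Where given, ranges in brackets use the visit windows.

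| Assumed sequence | Up to extra dose | After it | SAP rule |
|---|---|---|---|
| 1. Positive D35, negative D60, extra dose, positive D104 | 60 − 35 = 25 (55 − 37 = 18 to 65 − 33 = 32) | still open | at least 104 − 35 = 69 (94 − 37 = 57 to 114 − 33 = 81) |
| 2. Positive D14, negative D35, extra dose, positive D104 | 35 − 14 = 21 (33 − 15 = 18 to 37 − 13 = 24) | still open | at least 104 − 14 = 90 (94 − 15 = 79 to 114 − 13 = 101) |
| 3. Positive D14, negative D35, extra dose D50 (pre-dose negative), positive D60, negative D104 | 21 | 104 − 60 = 44 | 104 − 14 = 90 |
| 4. Positive D7, negative D14 to D60, extra dose D70 (pre-dose negative), positive D104, negative D134 | 14 − 7 = 7 | 134 − 104 = 30 | 134 − 7 = 127 |
| 5. Positive D35 and D60, negative D104, extra dose D120, no later positive | 104 − 35 = 69 | none | 69 |
| 6. Positive at every visit D35 to D104, extra dose D70 | at least 70 − 35 = 35 | still open | at least 104 − 35 = 69 |

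In sequence 3 the 90 days are 21 + 44 plus a 25-day negative gap (60 − 35). In sequence 4 the 127 days are 7 + 30 plus a 90-day gap (104 − 14). Sequence 5 shows that nothing changes without a post-dose positive. Sequence 6 shows why the overall duration must stay: cutting at the dose alone would shorten a continuous response.

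**How many patients?** 0.05 × 45 = 2.25 responders per arm at the planning rate. None were seen in the 141 earlier subjects. Only patients negative before the extra dose and positive after it have merged episodes, and that share cannot be computed from the documents.

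**The case against.** Measuring from the first positive to the time point after the last is an explicit, reproducible definition of total detectable span, and little depends on it. Duration appears only per patient in a listing, with no summary table and no between-arm statistic.

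A reader might infer from Protocol 5.2 that transient responders would be reported as persistent. The documents do not support that. The same section says both kinds are to be combined for overall immunogenicity, and no endpoint or SAP derivation classifies patients that way. A reader might also infer that the SAP leaves unscheduled samples out of duration. It does not: they fall under all samples after Day 0 pre-dose, and only the split is missing.

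A sample after the extra dose is not assured either. Monitoring is required until ADA returns to baseline, and in the merged case it already has. Unless a scheduled visit remains, nothing obliges a further sample. Sequences 1 and 2 give lower bounds, not finished values. Protocol 9.1 also allows results from additional unscheduled visits to be reported separately.

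Finally, the sequence can largely be seen already. Titer plots use sample dates, visits are labelled ADA-V1 and so on (SAP 7.2), with the nominal visit shown on the plot axis if possible, and samples and doses are listed.

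All of this stands and limits the consequence. It does not make the derived value mean what a reader of the listing would take it to mean. Sequences 3 and 4 show that the rule can return a completed, merged figure.

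**Conclusion.** The point holds as a minor one. A positive sample after the mandatory extra dose lengthens the single listed duration and can merge a resolved response to the scheduled doses with a response to re-challenge: 25 days becomes at least 69, 21 becomes at least 90, or 21 and 44 become 90.

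This rests on three assumptions: the extra dose falls after the negative sample, a later sample is taken, and that sample is positive. Where no later sample is positive, the SAP duration is unchanged. The effect is confined to a descriptive value in listing 16.2.6.5 for about 2 responders per arm, possibly none.

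It would be wrong to extend the point to the primary endpoint. A patient already counts as a responder before the extra dose is given, so incidence and onset cannot be affected through this route.

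**What to change.** In SAP 12.3.3, for both baseline groups, add a second derived duration. Apply the existing rule only to samples up to and including the pre-dose sample of the first unscheduled visit at which trial medication was actually administered. If that sample is still positive (for boosted patients, still at least 5-fold over baseline titer), report the value as at least x days. Keep the overall duration beside it in listing 16.2.6.5 and flag it when it spans an extra dose. Without an extra dose the two values are equal. A dose marker on the titer plots is optional.

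The cost is one derived column and one flag, from data already collected. Protocol 10.1 allows SAP adaptations before unblinding; after database lock the column would be labelled post hoc, as SAP 6 requires. The downside is a censored value for patients still positive at the extra dose, for whom the retained overall duration still shows the full span.
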